## 7.2 Screening and Critical Baseline Assessments

### Informed Consent Procedure

Signed, written, dated informed consent must be obtained from each potentially eligible subject before any study specific procedure is undertaken. The research team leaders will meet commanders and troops to explain the concept and importance of voluntary informed consent prior to inviting subjects to participate in the study. The person obtaining written consent must be independent of the subject to ensure consent is voluntary (i.e not the subject's commander or supervisor) to avoid perceptions of coercion or undue influence on a military subject. The subject's commander or supervisor must not be in the room during the consent process. Informed consent will be obtained on an individual basis, rather than as a group, ensuring that each subject has the opportunity to ask questions about the study.

Following informed consent, the following clinical and laboratory assessments will be conducted as described below (see Time and Events Table Section 7.1)

#### a) Procedures to be performed prior to DHA-POP administration

- Demographic data will be collected to include details of year of birth, gender, race and ethnicity.
- Medical history will be collected including cardiovascular history and associated risk factors.
- A physical examination will be conducted including:
  - Cardiovascular examination
  - Abdominal examination including an assessment of splenomegaly
  - Respiratory examination
- Vital signs will be assessed including height, weight, systolic and diastolic blood pressure, temperature (oral, axillary or tympanic), heart rate and respiratory rate. The same methodology should be used for measurement of temperature for all subjects.
- Investigators will assess *P. vivax* malaria symptoms at baseline. The incidence and severity (defined as absent, mild, moderate, severe, or unknown) of the following symptoms will be recorded: chills and rigours, headache, dizziness, abdominal pain, anorexia, nausea, vomiting, diarrhea, pruritis or itching, and coughing. The date of onset of symptoms will also be recorded. The investigator or designee can also assess and record any other *P. vivax* malaria symptoms.
- Blood smears for parasitological assessment will be collected and examined for asexual parasite count and gametocyte blood count (see Section 7.4 and the SRM for further details).
- Current and prior medications will be reviewed including any anti-malarial medication that has been used.

- A blood sample will be collected for *Plasmodium* genotyping analysis. An additional blood sample will be collected for future exploratory plasmodium whole genome sequencing (if parasite counts allow) (See Section 7.4 and Section 7.7).
- G6PD status will be assessed using the Fluorescent Spot Test (FST) or other suitable Point of Care Test (see SRM) to determine the subject's eligibility. An additional Point of Care Test (in development) may also be performed but the results of this test would not be used for eligibility. The quantitative spectrophotometric G6PD analysis will also be performed but results will not be available at the time of randomization. If results are discordant, the subject will be reviewed and appropriate G6PD testing will be repeated.
- Hematology and clinical chemistry assessments will be performed (refer to Section 7.5.5).
- Methemoglobin levels will be assessed using a non-invasive machine. This assessment will be performed by an independent person who will not participate in any other study procedures at the site. The data will be transmitted securely to GSK data management and will not be shared with other site staff unless result is above a preset threshold that requires a safety assessment (refer to SRM).
- A12 lead ECG will be performed with the subject in a semi-supine position having rested in this position for at least 10 minutes beforehand. Measurements that deviate substantially from previous readings will be repeated immediately. Three (3) measurements will be taken at screening, five minutes apart.
  - The mean heart rate, RR interval, QRS duration, uncorrected QT interval and QTcF (QT corrected by Friderica's formula) will be calculated from automated ECG readings and abnormal findings will be recorded in the eCRF. The mean value recorded pre-DHA-PQP will be classified as baseline.
- A blood sample will be collected for CYP2D6 genotyping and possible G6PD genotyping. The extracted nucleic acid sample for G6PD genotyping will be stored and may be analyzed in the event of an SAE due to hemoglobin decline where a repeat G6PD phenotype assay would not define G6PD status (e.g. transfusion given or high reticulocyte count).
- Subjects who have undergone screening and meet the label requirements for DHA-PQP dosing can receive open label DHA-PQP if the clinician deems that appropriate (e.g. symptomatic disease), and at least 3 hours have elapsed since last food intake. Thus, DHA-PQP may be commenced whilst the results of the hematology, clinical chemistry or G6PD deficiency screening tests are pending. Once these laboratory test results are available and the subject eligibility is confirmed, they will be randomized via the IWRS to blinded study treatment. The first dose of blinded study treatment will be administered with food at least 3 hours after DHA-PQP on Day 1 or Day 2.

### 7.3 Unscheduled Visits

Subjects will be encouraged to return for an unscheduled visit if they feel unwell or develop a fever at any time during the 180 day study period. The subject should be assessed for any adverse events and other procedures conducted as clinically indicated in order to diagnose/rule out malarial recurrence or explain other symptoms and signs.

### 7.4 Efficacy

#### Parasitology

- **Asexual parasite counts**

Microscope blood slides will be prepared prior to the first dose of DHA-PQP at screening on Day 1 to confirm the diagnosis of *P. vivax* malaria, and then twice a day, 6-12 hours apart for the first 3 days, or until 2 consecutive negative thick blood smears are obtained. Where the subject receives DHA/PQP < 6 hours from midnight on Day 1, a second Day 1 slide may be omitted.

Microscope blood slides will be prepared at subsequent visits on Days 7, 14, 21, 28, 60, 90, 120, 150 and 180 (refer to Section 7.1 Time and Events table). In addition, blood films should be obtained whenever parasitological re-assessment is required and at the relapse visit or withdrawal visit as applicable. For detailed instructions on the methodology for staining and counting please refer to the SRM.

Slides are considered negative after review of 100 high-power fields. A negative slide refers to the absence of asexual parasites only.

- **Gametocyte counts**

In the same way, thick film slides will be read for gametocytes on Day 1 (prior to the first dose of DHA-PQP) and then twice a day 6-12 hours apart for the first 3 days or until 2 consecutive negative thick blood smears are obtained. Slides will be prepared at subsequent visits on Days 7, 14, 21, 28, 90, 120, 150 and 180 (refer to Section 7.1 Time and Events Table).

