- Blood smears will be done twice daily, 6-12 hours apart until two consecutive negative smears are obtained. Additional blood smears will be done throughout the treatment and follow up period and on recurrence (if applicable).
- An on-site clinic will be established at the army base, which will be available 24 hours a day and 7 days a week for the duration of the study.
- Blinded study treatment will be administered daily, directly observed by site staff, for 14 days.
- Duration of study: Up to 195 days, including screening (Day 1) and randomization to treatment (Day 1 or Day 2), 14 daily visits while receiving blinded study treatment and seven follow-up visits (Days 21, 28, 60, 90, 120, 150 and 180). Subjects who do not relapse by Day 180 will attend a follow up visit on Day 195, following 14 days of open label primaquine.
- *Plasmodium* PCR genotyping will be performed on all baseline samples and in subjects who relapse to explore the proportion of heterologous and homologous relapses using appropriate PCR markers as well as define baseline genetic variability. Parasite whole genome sequencing will also be performed in a similar fashion, if parasite counts allow; these data will be reported separately.
- Subjects will be closely observed throughout the study by clinical and laboratory investigations including vital signs, ECGs, routine hematology/clinical chemistry and peripheral blood methemoglobin (metHb) levels at selected visits. This allows subjects who have a recurrence (e.g. those that happen to be randomized to the DHA-PQP alone arm) to be rapidly identified and safely managed minimizing the risk of serious clinical consequences of recurrence.
- MetHb will be determined by an independent assessor to avoid any potential for unblinding following 8-aminoquinoline dosing (refer to SRM).
- Subjects will be asked to report to the clinic at any time of the night or day should they feel unwell or develop a fever. Any subject diagnosed with recurrent *P.vivax* malaria (defined as a positive blood smear with or without vivax symptoms) will receive an ACT plus PQ 0.5mg/kg daily for 14 days and will be requested to continue to attend the scheduled study visits through to Day 180.
- Blood samples for TQ pharmacokinetic analyses will be drawn at the following times: pre-dose, 6-12 hours and 24-48 hours post blinded study treatment, Day 7, Day 14, Day 28, Day 60 or at relapse (up to 60 days post dose).

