## Time and Events Table (Continued)

Procedures	Visit Day (Follow Up Period)									
	21	28	60	90	120	150	180	195 p (only for subjects who have not relapsed prior to Day 180)	Relapse	Withdrawal from study
Window	-/+3d	-3d, +15d	-16 d, +15d	-14d, +15d	-14d, +15d	-14d, +19d	-/+10d	Day 180 + 15d to 21d		
Efficacy Assessments										
Parasitological Assessment (blood smears)	x	x	x	x	x	x	x		x	x
Plasmodium PCR genotyping/sequencing									x	
Safety Assessments										
Concomitant Medication	x	x	x	x	x	x	x	x	x	x
Physical Examination	x	x	x	x	x	x	x		x	x
Vital Signs d	x	x	x	x	x	x	x		x	x
12-lead ECG e		x							x	x
Adverse Events	x	x	x	x	x	x	x	x	x	x
Serious Adverse Events	x	x	x	x	x	x	x	x	x	x
Dispense rescue treatment (ACT+PQ)									x	
Laboratory Assessments										
Hematology/Clinical Chemistry	x	x	x	x	x				x m	x m
Methemoglobin l	x	x	x						x	x
PK Sampling		x	x						x n	
Open Label Primaquine										
Dispense open label PQ –only for subjects who have not relapsed prior to D180							x			

Time and Event Table Notes:

- a) Blinded study treatment may be started on Day 1 or Day 2. If started on Day 2, blinded primaquine/placebo is given from Day 2-15.
- b) If a subject starts blinded study treatment on Day 2, the following assessments should be completed on Day 15: Concomitant medication, AEs/SAEs, methemoglobin, dispense blinded study treatment.
- c) Blood smears to be taken twice daily until two consecutive negative smears 6-12 hours apart.
- d) Vital signs include height and weight (screening only), blood pressure, temperature, heart rate and respiratory rate.
- e) ECGs will be done in triplicate on Day 1 (prior to DHA-PQP). Subsequent ECGs will be done as single ECGs unless prolonged QTcF is seen. ECG timings post baseline will be as follows: 1) Before the last of the three daily doses of DHA-PQP 2) 4 hours (window -1 to +2 hours) after last dose of DHA-PQP, 3) Day 7, 4) Day 28 and 5) relapse/withdrawal if within 28 days post-dose.
- f) Adverse events are recorded from the time of the first dose of study treatment.
- g) Serious adverse events are recorded from the time of consent in order to fulfil international regulatory requirements.
- h) G6PD phenotyping to be performed by suitable qualitative test (refer to SRM) and quantitative spectrophotometric analysis.

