7.2.5.1. Statistical Methodology Specification

Secondary Statistical Analyses
Endpoints / Variables
Relapse-free efficacy at 4 months

Secondary Statistical Analyses

Time to relapse Time to fever clearance Time to asexual parasite clearance Time to gametocyte clearance

Model Specification

mITT population Estimates for time to endpoint will be determined for each treatment group using Kaplan-Meier methods. Cox's proportional hazards analysis, including terms for battalion and treatment for calculation of Hazard Ratios for time to fever clearance, time to asexual parasite clearance, time to gametocyte clearance, and relapse-free efficacy at 4 months.

Model Checking & Diagnostics

The proportional hazards assumption should be assessed including a check of the Kaplan-Meier curves. The shape of the curves should be similar for the treatment groups with the separation between the curves remaining proportional across time. A complementary log-log plot may also be used to check the proportional hazards assumption. If the proportional hazards assumption is violated a logistic regression model will be performed instead using a binary response variable of event vs no event (e.g. fever clearance vs no fever clearance) and including battalion and treatment as covariates.

Model Results Presentation

Time to relapse is covered in Table 2.8. Tables 2.16 to Table 2.19: Number of participants with the endpoint and number censored Estimates for time to the endpoint: 1st quartile, median, 3rd quartile and associated 95% confidence intervals For the relapse-free efficacy at 4 months endpoint only, the Kaplan-Meier estimate and 95% confidence interval of the relapse-free efficacy rate for each treatment at 4 months. For time to parasite clearance, time to fever clearance and relapse-free efficacy at 4 months: Hazard ratio (TQ+DHA-PQP vs DHA-PQP only, TQ+DHA-PQP vs PQ+DHA-PQP and PQ+DHA-PQP vs DHA-PQP only) and 95% confidence interval. Kaplan-Meier survival curves will be produced for time to fever clearance (Figure 2.5), time to asexual parasite clearance (Figure 2.6), and time to gametocyte clearance (Figure 2.7).

Subgroup Analyses

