
¹ For the twice daily blood smears on days 1-3, when determining exclusion from the PP population, participants were excluded if they didn't have at least one assessment on each day, without having first demonstrated clearance. The time of the assessments will not be used since visit windows around the 6-12 hour duration have not been defined.
 
² On study days 1-3, participants were scheduled to have twice daily blood smears until they had two consecutive negative smears, 6-12 hours apart. Due to errors in the parasite counts, 3 participants (participant numbers P_n PP and PP) were incorrectly concluded to have negative smears which were in-fact positive, and hence missed a subsequent parasitology assessment during days 1-3. These participants will not be excluded from the PP population as a result of this missed assessment.
	

During the study, the data is reviewed on an ongoing basis, with protocol deviations (PDs) identified by programmatic checks and manual review. These deviations are

assessed by data management and clinical (with input from others as required), and are entered into the deviations log, with the 'Important' flag set accordingly.

The per protocol population exclusion flag is a derived variable in the analysis and reporting dataset (ADaM.ADDV). This variable is not captured in the SI or SDTM datasets. As for the 'important PD' flag, data is reviewed throughout the study to identify participants who should be excluded from the PP population. At DBR, additional programmatic checks are performed by the clinical programming team to further check for PDs. A spreadsheet of any PDs identified is provided to data management and clinical, who will add them to the deviations log with appropriate flags if not already included.

A listing will be produced for the safety population showing the individual participant numbers for each important protocol deviation. A table will be produced showing the number and percentage of participants with major protocol deviations, overall and by type of deviation.

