
Defined as: time needed to clear asexual parasite from the blood i.e. parasite numbers falling below the limit of detection in the thick blood smear and remaining undetectable ≥ 6 hours later.
 
If a participant has a non-zero asexual P. vivax parasite count at baseline, and prior to Study Day 8 has two negative counts with at least 6 hours between the counts and no positive parasite counts within this time period, parasite clearance time will be defined as the time elapsed between the first dose of study medication (including DHA-PQP) and the first of these negative counts (measured in hours).
 
Participants with a negative parasite count at baseline will be censored with a parasite clearance time of 0 hours. All other participants will be censored at the time of the last non-missing assessment prior to Study Day 8.

Gametocyte (GCT)

Defined as: time from first dose until the first slide that was gametocyte negative and remained so at the next slide reading.
 
Any participant with negative P. vivax gametocytes at baseline will be censored with a time to gametocyte clearance of 0 days.
 
For all other participants, gametocyte clearance will be considered to have been achieved once a negative gametocyte value has been seen, unless the next gametocyte count is positive. Time to clearance will then be defined as (time to first negative value) – (time of first dose of study medication including DHA-PQP).
 
Subjects who fail to reach this endpoint will be censored at the visit of their final gametocyte assessment.

Fever (FCT)

Defined as: time from first dose of treatment to the time when body temperature falls to normal and remains normal for at least 48 hours up to the Day 7 visit.
 
Any participant who does not have a temperature in excess of 37.4°C at any point prior to the first dose of study medication (including DHA-PQP) on Study Day 1 will be censored with a fever clearance time of 0 hours. Participants will also be censored at time 0 if the method of temperature measurement is not consistent throughout Study Days 1 to 7 (i.e., method is not consistently oral, tympanic, or axillary).
 
Fever clearance is considered to have been achieved once an initial temperature of >37.4°C is reduced to a value $\leq 37.4^\circ\text{C}$, in the absence of value >37.4°C in the following 48 hours

Clearance time

up to the Day 7 visit.

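### Gametocyte clearance is analysed as an exact time in hours, although smears appear to stop on an asexual-only criterion and resume on Day 7

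*Protocol*

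**What the plan says.** Protocol 7.4 (Parasitology) has asexual slides made "twice a day, 6-12 hours apart for the first 3 days, or until 2 consecutive negative thick blood smears are obtained". It adds: "A negative slide refers to the absence of asexual parasites only". The gametocyte paragraph follows, is introduced as working in the same way, and repeats the two-negative stop without a gametocyte criterion of its own. Protocol 4.1 has the rule as "Blood smears will be done twice daily, 6-12 hours apart until two consecutive negative smears are obtained", and note c of the Time and Events Table as "Blood smears to be taken twice daily until two consecutive negative smears 6-12 hours apart". After the early smears the next scheduled slide is Day 7.

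The SAP lists time to gametocyte clearance as a secondary endpoint (7.2.1). Section 11.6.3 defines it as "time from first dose until the first slide that was gametocyte negative and remained so at the next slide reading" and censors men without gametocytes at baseline at time zero. Section 7.2.5.1 plans Kaplan-Meier estimates and a Cox model with battalion and treatment for "time to fever clearance, time to asexual parasite clearance, time to gametocyte clearance, and relapse-free efficacy at 4 months". Table 2.18 and Figure 2.7 report the result in hours, and the shell assigned to Table 2.18 (TTE3) has rows for quartiles, hazard ratios, confidence intervals and p-values. Nothing allows for the gap before Day 7.

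**The concern.** The disappearance of one parasite stage decides when the other stop being observed. A man whose asexual parasites clear quickly loses his remaining early slides. If his gametocytes clear a few hours later, his event time is recorded at Day 7. A man with the same gametocyte clearance but slower asexual clearance keeps his early slides and is recorded on Day 2 or 3. The recorded time then mixes gametocyte clearance with the smear schedule, and faster asexual clearance gives the later record.

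What is at stake is how Table 2.18 and Figure 2.7 are read: quartiles in hours that may describe the visit calendar, and a hazard ratio that could pick up a difference in asexual clearance if there is one.

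**Working it through.** The plan gives no figure for gametocyte clearance, so there is none to reproduce. The check has three steps.

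**1. Does the text produce an early stop?** Set side by side, Protocol 7.4 defines negative by asexual parasites only, and Protocol 4.1 and note c both stop at two negative smears. SAP Appendix 1 shows the rule being used that way: three participants were "incorrectly concluded to have negative smears which were in-fact positive, and hence missed a subsequent parasitology assessment during days 1-3". If smears always ran through Day 3, a wrong negative reading would not have cost them an assessment.

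**2. One man at a time.** Let T_a and T_g be the true asexual and gametocyte clearance times. Early slides run up to the second consecutive slide at or after T_a, and the next is Day 7 at 6 × 24 = 144 h. The recorded time is the first slide at or after T_g. Slide spacing (12 h here) and clearance times are assumptions.

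| True T_g | T_a = 12 h | 24 h | 36 h | 48 h | Slides kept to 72 h |
|---|---|---|---|---|---|
| 40 h | 144 | 144 | 48 | 48 | 48 |
| 50 h | 144 | 144 | 144 | 60 | 60 |

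For example, with T_a = 24 h the slides at 24 and 36 h are asexual-negative and smears stop. Gametocytes that clear at 40 h are next looked for at 144 h. With T_a = 36 h the second negative slide is at 48 h, and 48 h is recorded. The same true clearance is recorded 144 − 48 = 96 h apart (T_g = 40 h) or 144 − 60 = 84 h apart (T_g = 50 h). Spacing of 6 or 8 h gives the same pattern.

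**3. A group of carriers.** Simulation, with every input assumed: slides at 8, 24, 32, 48 and 56 h, then 144 h; gametocyte clearance SD 10 h; asexual clearance SD 8 h; the two independent.

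Gametocyte clearance mean 36 h:

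| Mean asexual clearance | Recorded at Day 7 | Recorded mean | Recorded median |
|---|---|---|---|
| 16 h | about 61% | 100 h | 144 h |
| 24 h | 38% | 78 h | 48 h |
| 32 h | about 15% | 57 h | 48 h |

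If slides instead continue to 56 h whatever the asexual reading, about 2% fall at Day 7 and the recorded mean is 44 h in all three rows. The early stop, not the slide spacing, accounts for most of the shift.

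Gametocyte clearance mean 24 h: about 4–22% are recorded at Day 7 over the same asexual range (12% at 24 h).

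The upper quartile reaches 144 h when more than 25% are recorded at Day 7, and the median when more than 50% are. So the upper quartile moves in the first two rows (61% and 38%) and the median only in the first. Neither moves in the third row, or anywhere in the 4–22% range.

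**Between arms.** With gametocyte clearance identical in two arms (mean 36 h), the hazard ratio is about 1.0 if mean asexual clearance is equal, about 0.92 for a 2 h difference, 0.86 for 22 versus 26 h, and about 0.75 for 18 versus 26 h. The last figure weakens to 0.82 or 0.86 if gametocyte clearance averages 28 or 24 h.

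**The case against.** The wording can be read otherwise. Protocol 7.4 could mean that smears run through Day 3 regardless, and negative under the gametocyte heading could mean gametocyte-negative. Detailed slide instructions are in the Study Reference Manual, which is not available here. This keeps the point at the likelier reading rather than a certainty, but the asexual-only definition and the three men in SAP Appendix 1 favour it.

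The endpoint is minor. It is in neither document's table of objectives and endpoints, and enters at SAP 7.2.1. Only baseline carriers inform it, and their number is not given. This stands.

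A reader might infer that the treatment hazard ratio is biased, and in the wrong direction. The documents do not support that. All arms receive the same open-label DHA-PQP from Day 1, blinded drug follows at least 3 hours later and may start on Day 2, and Protocol 4.4 describes tafenoquine as absorbed more slowly than ACTs. Nothing suggests that arms differ by 8 h in asexual clearance. Equality is not shown either, since blood-stage efficacy is itself a secondary objective, so the bias is conditional.

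A reader might also infer that the quartiles generally jump to 144 h. They do so only in some scenarios, and gametocyte clearance time, the input that matters most, is nowhere in the documents.

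**Conclusion.** The point holds in a limited form. On the likelier reading of Protocol 7.4, carriers still gametocyte-positive at their second asexual-negative smear are next read on Day 7, and the SAP treats that reading as an exact time. The upper quartile per arm, and in some scenarios the median, can then be pushed to about 144 h by when smears stopped. With mean asexual clearance of 16 to 32 h, the share of carriers affected is about 15–61% for a mean gametocyte clearance of 36 h and about 4–22% for 24 h. These are illustrations under assumed distributions, not estimates for this trial. Bias in the hazard ratio requires a between-arm difference in asexual clearance, which is not established. The primary endpoint, the relapse endpoints, asexual clearance and recrudescence rest on asexual counts and are not touched.

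**What to change.** In SAP 11.6.3 and 7.2.5.1, define gametocyte clearance as interval-censored between the last gametocyte-positive and the first gametocyte-negative reading. Use a Turnbull estimate for Figure 2.7 and the quartiles, and an interval-censored proportional hazards model for the hazard ratios in Table 2.18. In the 12-hour example with T_a = 24 h and T_g = 40 h, the man contributes the interval from 36 to 144 h instead of an event at 144 h. Report by arm how many baseline carriers were still gametocyte-positive at their last early smear, so that readers can see how much the gap matters.

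The cost is new SAP wording and a different procedure for one table and one figure. The reading times are already recorded (Listing 39, shell EFF_L2). There are two downsides. Intervals will be wider. Some bias may also remain, because reading times depend on asexual clearance, which may be correlated with gametocyte clearance within a man, whereas the standard interval-censored methods assume that the two are independent.

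SAP 2.1 records that 150 participants had already been randomised, so a change to the smear schedule cannot help men past Day 3. For any future participants, Protocol 7.4 and note c should state the stopping criterion for gametocyte reading separately from the asexual one.
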